## A Introduction

Falls are an escalating public health issue that drastically interrupt the healthy aging of older adults functionally and economically. Falls remain the leading cause of fatal death among older adults. Falls also cause an estimation of 2.8 million injuries and 800,000 hospitalizations annually. Exercise programs can effectively reduce falls by increasing balance and lower extremity muscle strength, but translation of these programs into clinical practice remains sparse. Older adults, especially those who live in medically underserved areas with few primary care providers and/or high rates of poverty are less likely to benefit from evidence-based exercise programs due to lack of exposure and access. Lack of translation and delivery of evidence-based interventions to medically underserved populations increase health inequities at the individual and community levels.

To fill this gap, we propose to adapt the Lifestyle-integrated Functional Exercise (LiFE) program for medically underserved older adults. LiFE has demonstrated high rates of fall reduction (31%) and adherence (80%) for community-dwelling older adults in Australia. This highly effective program uses habit formation strategies to enhance long-term behavior changes. Evidence, including our own preliminary data, suggest LiFE could be highly effective to reduce falls for medically underserved older adults, who commonly face economic hardship and other barriers to accessing health care. To address the cultural and behavioral differences between medically underserved older adults in the US and more affluent older adults in Australia, we will conduct a feasibility pilot study to test the feasibility of a randomized control trial (RCT) in preparation for larger trials for medically underserved older adults in the US.

### A1 Study Abstract

The purpose of this study is to pilot test the feasibility of a study design for future larger trial of Adapted LiFE among medically underserved older adults. We will evaluate if : 1) Adapted LiFE is feasible for medically underserved older adults, and 2) the study design is feasible with working randomization module and appropriate measurements.

Feasibility outcome measures include reach, acceptance, adherence, fidelity, safety, and appropriate efficacy outcome selection for balance, lower extremity muscle strength, and habit formation.

We will conduct a pilot RCT with an attentional control group. The treatment (Adapted LiFE) group (n=8) will receive 7-sessions of culturally Adapted LiFE over 12 weeks, while the attentional control group (n=8) will receive the same amount from an interventionist with a gentle flexibility program "Go4life" developed by the National Institute on Aging during intervention period.

We will recruit older adults who: are age 70 or older; self-report falls in the past 12 months; and reside in a medically underserved area. We will exclude participants who: have attention and memory impairment (Short Blessed Test score  $\geq 8$ ), are unable to stand with assistive devices, are severely depressed (The Geriatric Depression Scale  $\geq 10$ ), and have serious health conditions for which exercise is contraindicated. Paired t-tests will be used to test time effects, and independent t-tests will be used to test group effects of Adapted LiFE.

---

## **A2 Purpose of the Study Protocol**

The purpose of this study protocol is to establish a clear and detailed record of the objectives, design, methodology, statistical analysis plan to ensure the safety of the trial participants and integrity of the data collected.

---

## **B Background**

### **B1 Prior Literature and Studies**

Research has evaluated the efficacy of various fall prevention programs, and exercise has been shown to be one of the most effective interventions to reduce falls. However, evidence-based exercise programs encounter multiple barriers that lower the effectiveness of implementing interventions for medically underserved populations.

Medically underserved older adults are defined as older adults who live in a medically underserved area, designated by the US government with indicators of higher poverty level and fewer healthcare providers. Medically underserved older adults often belong to, but are not limited to, groups that have low income, are Medicaid-eligible, or are facing cultural or linguistic barriers to healthcare. Medically underserved older adults, who already experience more health inequities, are underrepresented in clinical trials, and evidence-based interventions are less likely to be designed to meet their needs.

It is also unknown whether exercise programs will translate to be effective for medically underserved older adults. To capture and describe the body of work on how medically underserved older adults are engaged in physical activity (PA) participation and whether exercise interventions have been specifically designed for this population, we have conducted a scoping review to explore and map the nature/extent of research conducted for medically underserved older adults. A total of 423 articles was identified with the search terms, 392 went through title and abstract review, 87 articles went through full text review. A final yield of 60 articles were included for data extraction. Twenty-one identified studies were intervention studies, only 4 of which specifically targeted underserved older adults aged 60 years and above. Three of these 4 studies were feasibility studies indicating that strategies to increase reach, retention, and adherence for medically underserved older adults are needed.

A gap exists in translating research into practice as few evidence-based programs have been implemented for low-income, minority populations. Challenges in translating evidence-based programs for these groups may result from uncontrolled moderating factors that hinder the implementation and effectiveness of evidence-based interventions. If health researchers leave these challenges unattended, health disparities are predicted to increase within a growing and increasingly diverse US population. To meet these challenges, we need to reduce implementation barriers early on in research design to ensure external validity for diverse populations.

### **B2 Rationale for this Study**

The Lifestyle-integrated Functional Exercise (LiFE) program has the potential to eliminate implementation barriers for medically underserved older adults through its design. LiFE is an evidence-based fall prevention program that embeds balance and lower extremity strength training activities into daily routines at home. We have targeted LiFE because it has strong face validity for medically underserved older adults and potentially controls for common moderating factors, such as time, resources, and

---

transportation constraints. Compared to structured exercise programs, LiFE provides a flexible and easy-to-adopt approach that can motivate medically underserved older adults who might otherwise perceive traditional exercise with highly structured routines as less appealing. LiFE demonstrated high rates of both adherence and fall reduction in previous clinical trials among Australian older adults.

However, we anticipate differences between our target population and the original LiFE participants. Differences in socioeconomic status and race/ethnic backgrounds will affect acceptance and uptake of the program, thus requiring adaptation of the original LiFE program to ensure external validity when generalizing research to a different population. It is critical to conduct a cultural adaptation process to achieve the goal of translating LiFE for medically underserved older adults.

Before investing large amount of resources and money into the main study, we aim to conduct a pilot study to assess the feasibility for a larger study design. The results of the feasibility pilot studies will inform researchers if it is reasonable to proceed with the main study.

## **C Study Objectives**

### ***C1 Primary Aim***

The primary aim of this study is to establish feasibility of Adapted LiFE and a RCT design.

WE hypothesis that the feasibility pilot study will have high reach (60% recruitment and 80% retention rate of targeted participants), acceptance (80% of participants rating high satisfaction with Adapted LiFE), adherence (80% of all exercise activities achieved during the intervention period for each participant), fidelity (90% consistency of elements delivered by occupational therapists throughout the study period), safety (no adverse events caused by Adapted LiFE), and appropriate efficacy measurement selection (70% of the participants do not show floor/ceiling effects among balance, muscle strength, and habit outcomes at pre- and/or post-tests).

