## **2.e Risks and Benefits**

### *Minimization of Risks and Confidentiality*

We are a HIPPA covered entity and comply with all HIPPA regulations. To protect against and minimize potential risks, participants will be carefully screened and evaluated for eligibility by research coordinator. Participants may have the risks of feeling tired or disrupted by home visits, sore muscles after practicing exercise activities, feeling worn out, or confidential information of participants may be accidentally disclosed. Participants may take a break at any time during participation and will be instructed to notify the rater or interventionist if they experience any discomfort.

An ID number will be assigned to each participant. All data collected from a participant will be labeled with the ID number. All participant electronic and hard-copy data will be kept under double-lock protection. All hard copy forms that contain personal identifiers (e.g., name, address, phone numbers) will be stored in a separate locked file drawer under double-lock protection. No publication or presentation of the study data will uniquely identify or provide sufficient information to uniquely identify participants.

To guard against unauthorized data access, all shared-use computer systems at the Washington University School of Medicine are protected with passwords, which are changed at 4-month intervals. Only individuals with a particular "need to know" status are given access, and system privileges are carefully restricted. All personal computers to be used in the Administrative Unit are located within a secure area, and the system is locked when not in use. SAS and SPSS software packages will be used for data management and analysis. Datasets generated from these programs will be password protected, which will make accessing study data difficult even in the event of unauthorized computer access occurs.

There is no proven benefit from being in this study. However, benefits to the participants enrolled in the proposed study are free in-home exercise sessions provide by OT interventionists. Participants in treatment group (Adapted LiFE) may be able to improve balance and muscle strength, and participants in the control group may be able to improve flexibility.

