### **3.a Treatment: Adapted LiFE**

Adapted LiFE teaches older adults to embed balance and lower extremity exercise activities into daily routines. The objective of LiFE is to form a habit to complete balance and muscle strength activities daily to improve balance and lower extremity muscle strength. A short summary of Adapted LiFE is at Table 2.

Participants will learn 10 exercise principles and 19 activities to increase balance and muscle strength during a 12 week intervention period (Table 3). For balance training, the core principle is to continue to practice a challenging balance activity, manage it, and then progress to another more challenging activity. For muscle strength training, the core principles are to overload muscles by adding weight, increasing repetitions, and moving slower to make the muscles progressively work harder.

Adapted LiFE is an intervention that aims to enhance self-efficacy through goal setting and creating appropriate outcome expectations to enhance participants' ability to repeatedly perform a target health behavior, which, in this case, is to form and adhere to a habit of exercise. Therefore, OT interventionists will guide participants to review the user manual and use a self-monitoring calendar (Adapted LiFE calendar) to plan and implement planned training activities.

The dose (visits and time) of Adapted LiFE consists of five weekly sessions and two booster sessions, which will be delivered by the OT interventionist in 12 weeks. Each session will last 40-60 minutes. The two booster sessions will be scheduled based on the needs of participants. If a participant has not finished learning all the activities after the fifth session, one or both booster sessions will be used to teach and implement the remaining activities, which will be conducted in the same manner as previous sessions. If a participant has completed learning all the activities, the first booster session (the 6th session) will be conducted with at least a two-week break after the 5th session. The second booster session (the 7th session) will be conducted at least a four-week break

---

after the 6th session. A phone follow-up call will be made after one month of the last intervention session as a booster session for participants to ask questions. feasibility outcome such as enrollment status, fidelity of intervention delivery will be documented by rater/interventionist log throughout the study period.

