#### **1.h Definitions of Adverse Events**

Adverse events are defined as any unfavorable and unintended diagnosis, symptom, sign (including an abnormal laboratory finding), syndrome or disease which either occurs during the study, having been absent at baseline, or if present at baseline, appears to worsen. Adverse events are to be recorded regardless of their relationship to the study intervention.

Serious adverse event (SAE). An SAE is generally defined as any untoward medical occurrence that results in death, is life threatening, requires inpatient hospitalization or prolongation of existing hospitalization, results in persistent or significant disability/incapacity, is a congenital anomaly or is another condition which investigators judge to represent significant hazards

---

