## ***F2 Study Outcome Measurements***

Feasibility outcomes include reach, acceptance, adherence, fidelity, safety, and appropriate efficacy outcome selection are described below. Feasibility outcomes will be assessed by the visit-by-visit grid, rater/interventionist log, the LiFE activity planner, and the feasibility questionnaire.

Reach is defined by recruitment and retention rate. Recruitment rate will be measured by the percentage of residents successfully enrolled in the study. Retention rate will be defined by the percentage of enrolled participants who complete the program. Reach will be documented by OT interventionists in interventionist logs and visit-by-visit grids in REDCap.

Acceptance will be surveyed by the feasibility questionnaire at the last session. The questionnaire contains a question, “Are you satisfied with the Adapted LiFE program?,” using a seven-point Likert scale from one (very unsatisfied) to seven (very satisfied). Follow-up questions will be asked to explore what makes the program satisfying or unsatisfying to the participant.

Adherence will be defined as the average percentage of exercise activities achieved during the intervention period that are recorded in the Adapted LiFE activity planner.

Fidelity will be assessed as the delivery of active and essential ingredients of the program as recorded by OT interventionists in visit-by-visit grids in REDCap. OT interventionists will meet weekly with the principle investigator to review the delivery of essential and active ingredients of Adapted LiFE for quality assurance.

Safety of the program will be evaluated by the number of adverse events documented throughout the study duration. This will be documented by OT interventionists in interventionist logs and visit-by-visit grids in REDCap.

---

The visit-by-visit grid is a checklist of all the elements that the interventionist should cover during each session. The interventionist will fill out the grid after every session is completed.

The rater/interventionist log is a survey that each rater/interventionist need to fill out after each visit to document any adverse event or special notes from a participant.

The LiFE activity planner is a weekly calendar for participants to fill out during the intervention sessions. Participants will record and check off the activities that they have completed.

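### The C1 safety criterion turns on adverse events caused by Adapted LiFE, but F2 counts all documented events and no causality step is described, so the criterion cannot be scored from the measure as written

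*Combined protocol and SAP*

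**What the plan says.** All references are to the combined protocol and SAP.

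- **Criterion (C1 Primary Aim).** One of the feasibility targets is "safety (no adverse events caused by Adapted LiFE".
- **Measure (F2 Study Outcome Measurements).** "Safety of the program will be evaluated by the number of adverse events documented throughout the study duration". Occupational therapy interventionists document this in their logs and visit grids.
- **Recording rule (F, 1.h).** "Adverse events are to be recorded regardless of their relationship to the study intervention". The definition covers "any unfavorable and unintended diagnosis, symptom, sign" and similar findings that are new or worse since baseline. It has no severity threshold and does not exclude anticipated reactions.
- **Listed risks (E2, 2.e).** "Participants may have the risks of feeling tired or disrupted by home visits", and the list continues with "sore muscles after practicing exercise activities, feeling worn out".
- **Handling of events (F, 1.i and 1.j).** Events are logged on the day of the visit or call. Two staff members discuss whether the participant needs to be withdrawn. An investigation is described only for a serious event that increases risk to participants.
- **Withdrawn participants.** Section 1.i deletes their data, apart from the reason for withdrawal and demographics. G4 says that all data are used for the feasibility outcomes, and F2 lists safety as one of these.

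**The concern.** A count of all events answers a different question from whether Adapted LiFE caused any. Moving from one to the other takes a causality judgement on each event, and the plan does not describe one.

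The gap matters in this population. E2 2.a enrols people aged 70 or older with two falls or one injurious fall in the past year, and the programme has them practise balance tasks in daily life. A fall during the study could be due to the practice or unrelated to it, and a bare count cannot tell the two apart. At the minor end, E3 3.a says that strength training aims to "overload muscles by adding weight, increasing repetitions, and moving slower", so some soreness is plausible. Nothing says whether it would count.

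Session-by-session documentation comes from interventionists who know the allocation (E3, 3.d). If attribution is left until the events are known, whether a primary criterion was met depends on a late judgement that is open to bias. B2 says that the pilot's results will inform whether to proceed to the main study.

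**Working it through.** **Step 1: criterion against data.** Scoring C1 needs three things: the events, the arm, and a causality call for each event. The first two are provided for. For the third, the places where it could appear are these:

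- F2 describes the log as capturing adverse events and special notes. It mentions no relatedness item.
- F 1.g assigns monitoring of adverse events, not attribution.
- F 1.i describes a discussion of individual events, but its stated subject is withdrawal.
- F 1.i and 1.j provide for an investigation, but only after a serious event that raises risk.
- G2 and G3 do not mention attribution of adverse events.

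No section supplies the causality call.

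**Step 2: can a listed reaction fail C1?** Soreness after practising is a symptom, is unfavourable, and could be absent at baseline. If it is also judged unintended and caused by the programme, it meets 1.h, and one report in one participant breaks a zero-event criterion. F 1.f refers to 2.e when discussing how adverse events are minimised, which supports reading the 2.e reactions as potential adverse events.

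**Step 3: how demanding is zero in 8?** The plan states no event rate or safety calculation, so there is no figure to reproduce. Inputs are n = 8 in the Adapted LiFE arm (A1 Study Abstract) and an assumed probability p that a participant has at least one related, recorded event. Participants are taken as independent.

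P(no related event in the arm) = (1 − p)^8

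| Assumed p | (1 − p)^8: C1 met | C1 not met |
|---|---|---|
| 1% | 92% | 8% |
| 5% | 66% | 34% |
| 10% | 43% | 57% |
| 20% | 17% | 83% |
| 30% | 6% | 94% |

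Failure becomes more likely than not when p exceeds 1 − 0.5^(1/8) = 8.3%.

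**Step 4: what a pass would show.** For 0 of 8, the exact two-sided 95% upper limit is 1 − 0.025^(1/8) = 37%. The one-sided 95% limit is 1 − 0.05^(1/8) = 31%.

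**Step 5: withdrawn participants.** Suppose one of the 8 is withdrawn and that record is deleted under 1.i. The count then rests on 7. At p = 10% the chance of zero is 0.9^7 = 48% instead of 43%, if withdrawal is unrelated to events. If the withdrawal followed an adverse event, the deletion could remove the event that would have failed the criterion. G4 read alone would keep it.

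**The case against.** Several counter-arguments have force.

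- **Recording everything does not conflict with C1.** It captures a superset from which caused events can be drawn. That is right, and the recording rule in 1.h is sound. What is missing is the rule for drawing them, and F2 still names the unfiltered count as the safety measure.
- **The log form is not in the text.** A relatedness field on it cannot be ruled out. This stands. Even with such a field, the text would still lack a named assessor, a rule, and a link from F2 to C1.
- **Events are reviewed promptly.** Same-day logging and staff discussion are prescribed, and the post-test and phone raters, who also complete logs, are blinded. So it is not established that attribution would be late or biased. The plan leaves that possibility open.
- **The pilot is descriptive.** G1 disclaims hypothesis testing, G2 plans descriptive statistics, and no formal stop/go rule is attached to safety. This limits the consequence. It does not make the criterion scorable.

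A reader might infer that soreness and tiredness are expected and that the criterion will therefore be failed, or waived afterwards. The documents do not support this. Section 2.e lists possible risks without any frequency and ties tiredness partly to home visits, which both arms receive. Whether soreness from deliberate muscle loading is unintended under 1.h can be argued either way. With no event rate given, a clean pass is quite possible at low p, and nothing in the text suggests a waiver.

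**Conclusion.** The point holds in a limited form. The stated safety measure does not answer the stated safety criterion, and the text gives no way of getting from one to the other. Whether a single minor reaction of the kind listed in 2.e counts against C1 is undecided, and one such reaction could settle the result.

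The size depends on an assumed event probability. Over p from 1% to 30%, the chance of meeting a zero-event criterion in 8 participants falls from 92% to 6%. Which end applies depends largely on whether minor reactions count, and that is exactly what the plan leaves open. The figures assume independent participants and all 8 retained in the count. The conclusion about the mismatch needs no rate and rests on the text alone, with the reservation about the log form.

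**What to change.** 1. Reconcile C1, F2, 1.h and 2.e, so that the measure in F2 is the one on which C1 is judged.
2. Add relatedness and expectedness fields to the rater/interventionist log, completed at the visit. Name who makes the attribution, preferably not the interventionist delivering the sessions, and on what scale. If the form already has such fields, say so in F2. Seriousness is already defined in 1.h.
3. State before enrolment whether the reactions listed in 2.e count toward C1, and tabulate them separately in either case.
4. Score C1 on related events in the Adapted LiFE arm, and report the number of participants with at least one event by arm. An exact interval is optional, but it would keep a result of 0 of 8 in proportion.
5. Reconcile the deletion of withdrawn participants' data in 1.i with the use of all feasibility data in G4, so that their adverse events stay in the safety count.

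The cost is two extra fields on an existing form, a few sentences of text, and a short prior agreement on what counts. Sample size and interventions do not change.

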## **2.d Randomization Method and Blinding**

After the consent process, the pre-test could be administered immediately or be scheduled at a different day. After pre-test, participants will be randomized immediately by a pre-programed REDCap (Research Electronic Data Capture) module. REDCap (Research Electronic Data Capture) is a secure, web-based application designed exclusively to support data capture for research studies. A blinded rater will conduct the post-test and phone follow-up.

Participants will not be blinded to which group they are in. The REDCap module uses a blocked randomization design in which gender will be stratified to ensure balanced group sizes. A block size of 2 and an allocation ratio of 1:1 based on gender. Then, based on group allocation, the occupational therapy (OT) interventionist will start either Adapted LiFE or the attention control intervention.

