## **G Statistical Analysis Plan**

### **G1 Sample Size Determination and Power**

The goal of the pilot is to test the feasibility of the Adapted LiFE for medically underserved population, and is not hypothesis testing. Thus, sample size calculation are not necessary. We select to set our sample size at 16 to evaluate feasibility and effect size for future study.

---

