## **G2 Analysis Plan**

Data will be entered into REDCap. Descriptive statistics will be used to identify any trends in demographics, and feasibility outcomes.

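### The primary-aim safety target can be met by zero attributed events in about 8 treated people, and the plan gives no upper bound to show how little that excludes

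*Combined protocol and SAP*

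**What the plan says.** C1 (Primary Aim) lists the feasibility targets that the investigators hypothesise the pilot will reach. One of them is "safety (no adverse events caused by Adapted LiFE".

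A1 gives the arm in which such an event can occur: "The treatment (Adapted LiFE) group (n=8) will receive 7-sessions of culturally Adapted LiFE over 12 weeks". G1 fixes the total by choice: "We select to set our sample size at 16 to evaluate feasibility and effect size for future study". It gives no precision target, because the pilot is described as not testing hypotheses: "Thus, sample size calculation are not necessary".

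On measurement, F2 says: "Safety of the program will be evaluated by the number of adverse events documented throughout the study duration". On analysis, G2 says: "Descriptive statistics will be used to identify any trends in demographics, and feasibility outcomes". No section plans a confidence interval or an upper bound for adverse events, or names a tolerable rate. Adverse events are recorded in both arms, but no section sets one arm against the other.

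B2 says that the pilot's results will inform whether it is reasonable to go on to the main study, so the safety result has a stated use.

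**The concern.** The target is met when nothing is seen. In 8 people, seeing nothing is likely even when the true rate of attributed events is far from zero, and the plan includes no statement of that uncertainty. The population is aged 70 or older with two falls or one injurious fall in the past year (E2, Inclusion Criteria), and the larger trial would be planned for similar people. If the result goes forward simply as a safety target that was met, a reader will take more from it than 8 people can support.

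Two further features make the count itself uncertain:

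- C1 counts events caused by Adapted LiFE, while F2 counts all documented events. The documents do not say how causation is judged.
- Section F, 1.i deletes the data of withdrawn participants apart from demographics and the reason for withdrawal, and E2, 2.f withdraws participants after certain serious adverse events. A participant with a relevant event could therefore leave the analysed data. G4 says that all data will be used for feasibility outcomes, of which safety is one. The two statements do not agree.

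**Working it through.** **Inputs**

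- Treated arm: n = 8 (A1). This agrees with G1 and the 1:1 allocation in E2, 2.d: 16 × 1/2 = 8. The plan gives no other derived figure to reproduce.
- Possible variation in n: 2.d specifies "A block size of 2 and an allocation ratio of 1:1 based on gender". If both gender strata end with an odd count, the treated arm could be 7 to 9.
- Retention target: "60% recruitment and 80% retention rate of targeted participants" (C1). Applied to the treated arm, 8 × 0.8 = 6.4, so about 6 or 7 people.
- True event rates of 5%, 10% and 20%: assumed for illustration. The documents give none.

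All figures assume that participants are independent and that each is counted once, as having or not having an attributed event between enrollment and the one-month call (the reporting period in section F, 1.k).

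**What 0 of n leaves open.** The exact upper limit with zero events is 1 − a^(1/n), with a = 0.05 for a one-sided 95% bound and a = 0.025 for the upper end of a two-sided 95% interval. For n = 8:

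- One-sided: 1 − 0.05^(1/8) = 0.312, or 31%.
- Two-sided: 1 − 0.025^(1/8) = 0.369, or 37%.

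These bounds need no assumed event rate.

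**How often zero events would be seen.** The probability is (1 − p)^8:

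- p = 5%: 0.95^8 = 0.663, or 66%.
- p = 10%: 0.90^8 = 0.430, or 43%.
- p = 20%: 0.80^8 = 0.168, or 17%.
- p = 30%: 0.70^8 = 0.058, or 6%.

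**Sensitivity to the number analysed**

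| Treated people analysed | One-sided 95% bound at zero events | Two-sided 95% bound at zero events | Chance of zero events at p = 10% |
|---|---|---|---|
| 6 | 39% | 46% | 53% |
| 7 | 35% | 41% | 48% |
| 8 | 31% | 37% | 43% |
| 9 | 28% | 34% | 39% |

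The rows for 6 and 7 show what happens if non-completers drop out of the safety count at the plan's own retention target. They do not allow for participants leaving because of an event, which would make zero more likely still.

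**Scale.** For zero events to exclude a 10% rate, (1 − 0.10)^n must fall to 0.05 or below. That takes n = 29 treated people one-sided, or 36 at the two-sided level (0.025). This is no argument for a larger pilot. It shows how far 8 people are from supporting such a statement.

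**The case against.** The strongest reply is that no section declares Adapted LiFE safe on the strength of zero events. C1 states a hypothesis, G1 says the pilot does not test hypotheses, G2 promises description only, and B2 says only that results will inform the next step. That stands. A reader might infer from the 43% figure that a harmful program would be declared safe 43% of the time. The documents do not support this, because they contain no such declaration and no 10% rate.

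The breadth of the event definition also stands as an objection. Section F, 1.h counts any unfavourable and unintended symptom or sign, and E2, 2.e names sore muscles and tiredness as foreseeable risks. A 10% rate of any attributed event is therefore not a 10% rate of serious harm. With so broad a definition the strict zero target may well fail: at a 30% rate it would be met only 6% of the time.

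Nor does participant safety rest on this count alone. Section F, 1.g provides continuous monitoring of individuals. Sections 1.i and 1.j provide for a halt, an investigation and a findings report after a serious event that raises risk. D2 cites earlier LiFE trials as the basis for minimal risk, although B2 expects this population to differ from those participants.

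Finally, the other C1 targets are also bare thresholds without intervals, in the same small sample. That is true, and it keeps this a reporting point. It does not remove the gap: the absence of a power calculation is no reason to leave the uncertainty of a primary-aim criterion undescribed.

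**Conclusion.** The point holds as a minor one. The safety target can be reported as met on 0 of 8, and the plan includes nothing to tell the reader that this leaves open a per-person rate of attributed events of up to 31% (one-sided) or 37% (two-sided). The bounds rest on 8 independent treated participants, all kept in the count. If only 6 or 7 are analysed, the one-sided bound rises to 39% or 35%. The chances of seeing zero events (66%, 43% and 17%) depend on assumed rates and cover minor as well as serious events. They illustrate imprecision and should not be read as false-safe rates for serious harm. The fault lies in the missing bound, the missing interpretation and the unsettled numerator and denominator. A sample of 16 is not itself at fault in a feasibility pilot.

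**What to change.** - **C1:** word the target as *no adverse event attributed to Adapted LiFE observed*, and add that meeting it does not establish safety.
- **F2 and G2:** report the number of Adapted LiFE participants with at least one attributed event, over all who received any Adapted LiFE session, with the exact 95% upper bound and its sidedness stated (for 0 of 8, 31% one-sided or 37% two-sided). Show serious and non-serious events separately, and list all adverse events by arm.
- **C1 and F2:** reconcile caused events with all documented events, and state how attribution is judged, since the bound needs a defined numerator.
- **Section F, 1.i and G4:** amend the deletion sentence so that adverse event data of withdrawn participants are kept for this count, and reconcile it with the statement in G4 that all data are used. Without this change the proposed denominator cannot be applied.
- **Main trial:** any safety statement carried forward should quote the upper bound beside the count.

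The cost is a few sentences, a change to one data-handling rule and a one-line exact binomial calculation. No extra participants or visits are needed. The downside is a less favourable safety statement.
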